Study Centre(s)	
 1. Tobacco Dependence Research Unit, Wolfson Institute of Preventive Medicine, QMUL 2. East Sussex Stop Smoking Service (Quit 51) 3. Leicester Stop Smoking Service
Objectives	
Primary: To determine the 12-month sustained biochemically validated abstinence rates in smokers using EC compared to smokers using standard NRT.
 
Secondary: Abstinence rates at 4 weeks and 6 months, CO validated sustained abstinence rates between 6 and 12 months, effects of the two treatments on smoking reduction in participants who did not achieve full abstinence, changes in urges to smoke and other tobacco withdrawal symptoms at 1 and 4 weeks, ratings of the two treatment approaches by patients, rates of adverse reactions associated with the use of EC and NRT, cost-effectiveness of EC compared to NRT.

Number of Subjects/Patients	886 randomised participants
Main Inclusion/Exclusion Criteria	
Inclusion criteria: 18 years and older, current smoker accessing a stop smoking service, able to read/write/understand English.
 
Exclusion criteria: Pregnant or breastfeeding, strong preference to use or not to use NRT or EC in the quit attempt, currently using NRT or EC, already enrolled in interventional research.

Statistical Methodology and Analysis	
Abstinence rates and rates of those sustaining a 50% or greater reduction in baseline cigarette consumption and CO levels will be compared between the study arms using a Pearson Chi-squared test with logistic regression. Frequency of adverse reactions will be compared between arms. Time to relapse will be analysed using a Cox analysis. If no significant difference in abstinence rates is detected between the study arms then a non-inferiority analysis will be undertaken. Participants lost to follow-up or not providing biochemical validation will be included as non-abstainers.

GLOSSARY

AE	Adverse event
AR	Adverse reaction
CO	Carbon monoxide
CPD	Cigarettes per day
DMEC	Data Monitoring and Ethics Committee
EC	Electronic cigarette
EQ5D	European Quality of Life -5 Dimensions
FTND	Fagerstrom Test of Nicotine Dependence
JMRO	Joint Management Research Office
LOR	Letter of recommendation
MPSS	Mood and physical symptoms scale
NRT	Nicotine replacement therapy
QA	Quality assurance
QC	Quality control
RCT	Randomised controlled trial
SAE	Serious adverse event
SAR	Serious adverse reaction
SSC	Study Steering Committee
SSS	Stop Smoking Service

1.1 Background

Electronic cigarettes (EC) are battery-powered devices that provide inhaled doses of nicotine by delivering a vaporised liquid nicotine solution in propylene glycol or glycerol. No tobacco, smoke, or combustion is actually involved in their operation.

EC have largely been marketed as a 'lifestyle' product for smokers who want to reduce the risks of smoking. EC provide levels of nicotine similar to those provided by NRT, but they might have an advantage over existing NRT products because of their ability to provide more realistic sensorimotor and behavioural replacement for smoking.

Current smoking cessation treatments generally provide a combination of behavioural support and evidence-based medicines to target withdrawal discomfort, but sensorimotor factors are not well addressed. EC provide sensations similar to smoking a cigarette by emitting a smoke-like mist or vapour, and provide taste and throat sensations which are closer to smoking than those provided by oral NRT e.g. the nicotine inhalator. There is some evidence that these factors are important for smokers and that their inclusion enhances treatment efficacy [1].

1.2 Clinical Data

Our team has conducted a number of studies of EC [2–21] including some of the early research on EC showing that they could alleviate urges to smoke. At the time our first study was undertaken (2008-09) EC use was marginal, but it increased substantially over the following years. In the UK, current use in smokers increased from 2.7% in 2010 to 6.7% in 2012 [22].

Survey data consistently show that users report that EC help them to either quit or reduce smoking [12,13,22–24]. EC users are more likely to be current smokers than ex-smokers and use EC to quit or reduce risks of smoking [22,24]. They tend to be younger and better educated than other smokers [25,26].

Early pharmacokinetic studies showed that EC delivered low or no nicotine to the user [7,27,28]. However, these studies typically used short fixed puffing schedules and smokers without any experience in using EC. Some of the EC used were also of poor quality [7]. In later studies where users were able to familiarise themselves with the product and/or use it for longer periods, plasma nicotine delivery was comparable to that from oral NRT products (e.g. 4-5ng/ml) [29,30]. In experienced EC users increases of up to 13 ng/ml have been observed [9,31], which is similar to the changes seen after smoking a regular cigarette (e.g. 10-20 ng/ml [32]).

Several studies have now demonstrated that EC reduce urges to smoke after a period of abstinence [7,9,11,27–31].

Effects of EC on smoking

Several case studies have reported EC effectively helping people that have failed to quit with other methods [33–35]. Data from two prospective cohort studies and two RCTs give an indication of the potential for EC to help smokers reduce tobacco consumption and stop smoking.

Two reports [36,37], of the same study examined the effects of EC use in 40 highly dependent smokers unwilling to quit. Two years after enrolment, 28% had achieved a sustained $\geq 50\%$ reduction from baseline cigarette consumption, and an additional 13% achieved at least 6 months of CO validated abstinence from conventional cigarettes. The second study using the same approach with 14 smokers with schizophrenia reported that at 1-year follow-up, half of the participants had achieved a $\geq 50\%$ reduction of their baseline cigarette consumption for at least 30 days, and an additional 14% had achieved 30-day CO validated abstinence [38].

A double-blind trial of 300 smokers not intending to quit compared effects of EC containing 7.2mg or 5.4mg nicotine and a nicotine free EC provided for 12 weeks [39]. At one year, biochemically validated 6-month abstinence rates were 13%, 9% and 4% in the three groups. The difference between the three groups was not significant, but the two nicotine EC groups merged had a significantly higher quit rate than the non-nicotine group (11% vs. 4%, $p=0.04$). At one year, 27% of successful quitters (7/26) were still using EC, leaving the majority tobacco and nicotine free.

One RCT has evaluated the long-term effects of EC on smoking cessation in treatment-seeking smokers [6]. It compared nicotine-containing EC with 21 mg nicotine patches and with non-nicotine EC. In addition, participants were provided with a referral to a telephone Quitline but with no face-to-face contact. In this minimal support context, no significant differences across treatment arms was observed, with validated continuous abstinence at 6 months observed in 7.3% participants assigned to the nicotine EC, 5.8% assigned to the patch, and 4.1% assigned to the non-nicotine EC. Significantly higher self-reported smoking reduction and higher user endorsements were observed for the participants who received nicotine EC relative to those who received nicotine patch. The study was underpowered, used EC with low nicotine delivery, and the minimal support paradigm was not ideal for testing a new treatment. A commentary on the finding pointed out that because EC are more attractive than patches to many smokers, and can be accessed in most countries without the restrictions around medicines that apply to NRT or the costly involvement of health professionals, they have the potential to increase rates of smoking cessation and reduce costs to quitters and to health services [16].

EC safety

The most common side effects users reported were dryness or irritation of the throat and mouth [12,24,40,41]. Headache, cough, vertigo, nausea and palpitations were also reported.

None of the experimental [7,9–11,27,28,30,31] or prospective follow-up studies [36,38] reported serious adverse events (SAEs). Any AEs were largely mild to moderate and included symptoms such as mouth and throat irritation and dry cough, similar to those reported in user surveys. No significant difference in the frequency of AEs, between EC and control groups (non-nicotine EC or patch), were observed in the two randomised trials of EC [6,39].

Some commentators have expressed concern over the risk of nicotine poisoning with EC. These risks, however, are very low. We are aware of one report describing several suicide attempts, where adults drank up to 1,500 mg of nicotine in e-liquid (this is significantly greater than the often quoted lethal dose of 30-60 mg), which resulted in 'voluminous vomiting' and a full recovery within a few hours [42]. There is also a case report of an 18-month child who drank e-liquid and was admitted to

hospital with vomiting, ataxia, and lethargy, and was discharged after 24 hours of observation [43]. EC refill liquids now come in childproof bottles.

1.3 Rationale and Risks/Benefits

Data are urgently needed on whether EC match the efficacy of other existing treatments in helping smokers quit or reduce smoking. Several studies have suggested that EC have a substantial potential as a stop-smoking treatment but no study has compared EC to a standard intensive treatment so far.

Smokers now frequently ask the Stop Smoking Service (SSS) for advice on whether EC can help them quit smoking. In a survey of UK SSS managers, commissioners and advisers, the need for guidance on EC advice was the number one priority [22]. More recently the National Institute for Health and Clinical Excellence (NICE), in their guidance on Tobacco Harm Reduction, highlighted the critical need for outcome and safety research on novel nicotine-containing products, in particular EC [44].

EC are cheaper than a standard 12-week treatment course of NRT (and other prescription non-nicotine smoking cessation medicines), and hold greater appeal to smokers [6,7]. There are few other smoking cessation treatment improvements on the horizon and EC are the most promising current development awaiting objective scrutiny. In order to inform their practice, health care commissioners need to know if they are as effective as licensed nicotine smoking cessation medicines when used with the support routinely provided by the UK stop-smoking service. This proposal aims to provide this information.

EC use does not involve tobacco combustion, which is the primary source of the many thousands of dangerous chemicals to which smokers of conventional cigarettes are exposed. Studies on EC users have identified little or none of the known toxins associated with tobacco smoking [45], and while they may not be entirely safe, no serious health risks have been identified. There is little doubt they are substantially safer than conventional cigarettes, and they have the potential benefit of reducing urges to smoke and boosting rates of smoking cessation.

Electronic cigarettes have a potential to increase the reach and reduce the costs of the UK SSS. The aim of this trial is to determine if EC are more effective than standard NRT products when used with face-to-face behavioural support as provided by the SSS.

2 Trial Objectives and Design

2.1 Trial Objectives

Primary Objective - To determine the 12-month sustained, biochemically validated abstinence rates in smokers using EC compared to smokers using standard NRT.

Secondary Objectives -

1. Abstinence rates at 4 weeks and 6 months.
2. Abstinence rates between 6 and 12 months
3. Effects of the two treatments on smoking reduction in participants who did not achieve full abstinence.

4. changes in urges to smoke and other tobacco withdrawal symptoms at 1 and 4 weeks.
5. Ratings of the two treatment approaches by patients.
6. Rates of adverse reactions associated with the use of EC compared to standard NRT.
7. Cost-effectiveness of EC compared to standard NRT.

2.2 Trial Design

This is a pragmatic RCT where smokers who want help to quit smoking will be individually randomised to receive usual care (UC; a choice of NRT combined with usual care behavioural support provided by the SSS) or EC with the same behavioural support.

3 Subject Selection

3.1 Number of Subjects and Subject Selection

886 participants would be recruited from SSS. Participants would present to the clinics either in response to advertisements in local newspapers, through GP practices or following routine referrals.

3.2 Inclusion Criteria

- Aged 18 or over
- Current smoker accessing the SSS
- Able to read/write/understand English

3.3 Exclusion Criteria

- Pregnant or breastfeeding
- Strong preference to use or not to use NRT or EC in their quit attempt
- Enrolled in other interventional research
- Currently using NRT or EC

4 Study Procedures

4.1 Informed Consent Procedures

Potential participants will be informed of the study by SSS and research staff who will discuss the study, and if interested/eligible potential participants will be provided with written information, along with the standard SSS client registration form, prior to their first session. At the baseline session, study details would be discussed with clients interested in taking part and informed consent obtained by good clinical practice (GCP) trained members of the study team, who are delegated to do so on the delegation log.

4.2 Screening Procedures

Potential participants would be screened for eligibility during the baseline session.

4.4 Schedule of Treatment for each visit

Identical multi-session behavioural support will be provided to both groups. The exact procedures differ slightly between the different study sites, but usual care for smoking cessation involves face-to-face support sessions (Withdrawal Oriented Treatment [46]), which usually begin 1-2 weeks prior to the TQD. Clients attend weekly for several weeks after the TQD. Study data will be collected face-to-face at the first (baseline) session, the TQD, and for the first 4 weeks post-TQD.

Participants would also be contacted by telephone at 24 and 52 weeks post TQD to obtain smoking status and assess EC/NRT/other product use and adverse reactions; those who report abstinence or a reduction in smoking by at least 50% would be asked to provide a CO reading at 52 weeks.

Participants would be compensated £20 for their travel and time at the 52-week visit.

Control Group

Participants will be informed about the range of NRT products available at the baseline session. The supply of NRT differs slightly between the different study sites. For example, the Tower Hamlets SSS provides NRT via a letter of recommendation (LOR) to supply on a fortnightly basis for the first 4 weeks, which clients take to a pharmacist to exchange for NRT paying a prescription charge of £8.05, if applicable (some 50% of SSS clients are normally exempt from the charge) whereas East Sussex SSS provide NRT by direct supply at no charge. For those sites giving LORs, participants will be given an LOR at their baseline session (as per standard practice) and instructed to collect the NRT and bring it to their TQD session. At the TQD those randomised to the NRT condition will keep their NRT and have their first use during the session. For sites that provide NRT on direct supply, participants randomised to the NRT condition will be provided with their NRT during the TQD session. For all sites, detailed instructions on use and information on common side effects will be provided as part of the behavioural support. At the completion of the study treatment period participants can request further supplies of NRT in line with the SSS standard practice (for example, at the Tower Hamlets service, patients can request further 2 week LOR supplies of NRT up to a total of 12 weeks).

Intervention Group

Participants in the intervention group who are attending a site using LORs will also be given an LOR at their baseline session and will be asked to collect the NRT and bring it to their TQD session. Participants who are then randomised to the EC condition at the TQD will return their NRT in exchange for an EC starter kit (18mg/ml nicotine), which will include a two week supply of e-liquid and information on where to purchase more themselves. Participants in the EC condition will have an option to request a further 2-week supply of the liquid at 2 weeks post-TQD if they are using the supplied product and have not managed to buy their own e-liquids by this point. They will be provided with both verbal and written instructions on how to operate the EC. Participants will be advised on how to obtain further supplies themselves. They will be free to try other brands and at every contact point we will monitor which EC product is being used as well as the frequency and length of use.

At the TQD all participants will be asked to sign a commitment form stating that they will commit to using their allocated treatment, and will not use the non-allocated treatment, for at least the initial four weeks post-TQD.

[figure not shown]
4.5 Measures

- Demographic details, smoking and medical history
- Fagerstrom Test of Cigarette Dependence (FTND) [47]
- Mood and Physical Symptoms Scale (MPSS): Measure of severity of urges to smoke and other tobacco withdrawal symptoms [48]
- Self-reported smoking status
- End-expired carbon monoxide reading: Collected using a calibrated CO monitor. A reading of <8ppm would be used as a cut-off for abstinence
- Adverse reactions
- Use of EC/NRT and ratings of helpfulness to refrain from smoking and satisfaction in comparison to usual cigarettes. Participants who stop using EC will also be asked their reasons for doing so.
- European Quality of Life-5 Dimensions (EQ5D) questionnaire at baseline and at 6 and 12 months [49]
- Smoking cessation service and health service use at baseline and at 6 and 12 months

4.6 Study product (E-cigarette)

We will use a second generation EC with e-liquid containing 18mg/ml nicotine (the most commonly used nicotine content [45]). The EC will have a CE mark. Participants will then be directed to select and purchase their own refill e-liquid. They will also be able to purchase another EC brand on their own. This will (a) ensure that people use a refill e-liquid they like; (b) reflect what happens in 'real life'; and (c) avoid giving the EC arm an advantage of free treatment when some people in the UC arm will have to pay a prescription charge.

4.7 Flow Chart of Study Procedures

- Data collected as per the schedule of assessment below
- Participants lost to follow-up considered to be smoking
- **Analysis (n=443)**

- Data collected as per the schedule of assessment below
- Participants lost to follow-up considered to be smoking
- **Analysis (n=443)**

4.8 Schedule of Assessment

Measures/ Procedures	Study session							
	Baseline	TQD	TQD+1 week	TQD+2 weeks	TQD+3 weeks	TQD+4 weeks	TQD+24 weeks	TQD+52 weeks
Informed consent	X							
Baseline questionnaire	X							
Current illness	X		X	X	X	X	X	X
Current medication	X		X	X	X	X	X	X
Randomisation		X						
Commitment form		X						
CO validation	X	X	X	X	X	X		X (if report abstinence or at least 50% reduction)
MPSS	X	X	X			X		
Smoking status/CPD	X	X	X	X	X	X	X	X
Adverse reactions			X	X	X	X	X	X
EC/NRT ratings			X			X		
Quantity/dose of EC/NRT used and helpfulness		X	X	X	X	X	X	X
EC dispensed, demonstration on first use		X		X				
NRT* dispensed, demonstration on first use		X		X		X		
EQ5D questionnaire	X						X	X
Smoking cessation service and health service use	X						X	X

* Dispensing sessions may differ slightly between sites depending on local SSS practices

4.9 End of Study Definition

The study would be completed and the REC informed after the final attempt to collect 12 month follow-up data from the last randomised participant.

4.10 Subject Withdrawal

Participants will be able to withdraw from the study at any time. This will not put at risk their usual medical care. Unless withdrawn participants request otherwise, data collected up to the point of their withdrawal will be used in the study analysis. Participants will be withdrawn if they withdraw their consent to participate. We do not foresee any other reasons to withdraw participants.

4.11 Data Collection and Follow up for Withdrawn Subjects

Participants that withdraw from the study would be followed up at weeks 4, 24 and 52, unless they did not wish to be contacted.

5 Adverse event/reaction reporting

5.1 General Definitions

5.1.1 Adverse Event (AE) and Adverse Reaction (AR)

An AE is any untoward medical occurrence in a subject to whom the study product has been administered, including occurrences which are not necessarily caused by or related to that product. An AE can therefore be any unfavourable and unintended sign (including an abnormal laboratory finding), symptom or disease temporarily associated with the use of the study product.

All AEs judged by either the reporting investigator or the Sponsor as having a reasonable causal relationship to the study treatment qualify as an AR.

5.1.2 Serious Adverse Event (SAE) and Serious Adverse Reaction (SAR)

An SAE/SAR fulfils at least one of the following criteria:

- Is fatal – results in death
- Is life-threatening
- Requires inpatient hospitalisation or prolongation of existing hospitalisation
- Results in persistent or significant disability/incapacity
- Is a congenital anomaly/birth defect

5.2 Investigators Assessment

5.2.1 Seriousness

Adverse events/reactions will be assessed for seriousness according to the definitions given in section 5.1.2.

5.2.2 Causality

The causality of all serious adverse events/reactions will be assessed in relation to the trial treatment by the local PI and the CI. The following ARs are

deemed potentially related to the study treatment: nausea, throat irritation and sleep disturbance.

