5.3 Notification and reporting Adverse Events or Reactions

Data on ARs, SARs and SAEs will be collected. If the AR is **not** defined as SERIOUS, the AR will be recorded in the CRF and the participant will be followed up by the research team. All ARs will be documented in the CRF.

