5.4 Notification and Reporting of Serious Adverse Events/Reactions

All SAEs including SARs will be recorded in the subjects’ notes, the CRF, the sponsor SAE form and reported to the co-ordinating site. **Related and unexpected SAE’s should be reported to the sponsor at [contact] or by fax on: [name])** within 24 hours of PI or co-investigators becoming aware of the event. Nominated co-investigators can be authorised to sign the SAE forms in the absence of the CI at the co-ordinating site or the PI at the participating sites. The original and any subsequent follow up of SAE Forms together with the fax confirmation sheet must be kept with the investigator site file at the study site.

Additionally related and unexpected SAE’s will be reported to the Ethics committee within 15 days.

6 Statistical Considerations

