6.4 Statistical Analysis

Analyses will be undertaken after the last participant has completed the 12-month follow-up and the database has been locked.

For the primary analysis the proportion of people remaining abstinent at a year will be compared between the study arms using Chi-squared test with a secondary logistic regression adjusted for study site, sex, age, education, marital status, occupation, entitlement to free prescriptions, ethnicity, daily cigarette consumption, FTCD, age started smoking, partner smoking status, previous smoking cessation medicines used.

For the secondary analyses, we will examine the differences between study arms in the proportions of participants with sustained abstinence at 4, 24 and 52 week follow-up, and sustaining a 50% or greater reduction in baseline cigarette consumption and CO levels at 52 weeks, using Chi-squared test/logistic regression. The frequency of

adverse reactions will also be compared between arms. Between-group differences in urges to smoke and other tobacco withdrawal symptoms will be examined using ANOVA, controlling for baseline ratings. We will also examine time to relapse in a secondary analysis using a Cox analysis with model adequacy assessed by cumulative martingale residuals. An intention to treat analysis will be used with participants lost to follow-up or not providing biochemical validation included as non-abstainers [50]. A sensitivity analysis will be conducted with only participants who attended at least one treatment session from the TQD included.

Economic analyses

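### Non-serious events are recorded only after a relatedness judgement made with allocation visible, so the between-arm comparison of adverse reactions mixes harm with attribution

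*Protocol*

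**What the plan says.** Four parts of the Protocol bear on this point.

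- **Definition (5.1.1).** "All AEs judged by either the reporting investigator or the Sponsor as having a reasonable causal relationship to the study treatment qualify as an AR". An AR is therefore an adverse event that has already passed a causality judgement.
- **Collection (5.3, 5.4).** "Data on ARs, SARs and SAEs will be collected", and "All ARs will be documented in the CRF". Collection of non-serious events not judged related is not stated. Serious events are kept whatever their cause: "All SAEs including SARs will be recorded in the subjects’ notes, the CRF, the sponsor SAE form and reported to the co-ordinating site".
- **Causality (5.2.2).** "The causality of all serious adverse events/reactions will be assessed in relation to the trial treatment by the local PI and the CI". The section then names certain ARs as "deemed potentially related to the study treatment: nausea, throat irritation and sleep disturbance". It does not say what the list is for or whether it is complete.
- **Analysis (2.1, 6.2, 6.4).** AR rates under EC and NRT are secondary objective 6 and a secondary endpoint. Section 6.4 states that the frequency of "adverse reactions will also be compared between arms".

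The background on EC safety in 1.2 gives dryness or irritation of the throat and mouth as the commonest complaints and adds: "Headache, cough, vertigo, nausea and palpitations were also reported".

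No blinding is described. Under 4.4, at sites that use letters of recommendation, participants allocated to EC hand back their NRT for an EC starter kit at the quit-date session, so staff and participants know the allocation.

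**The concern.** A between-arm comparison of event rates is interpretable when events are ascertained in the same way in both arms. Here the outcome is defined by a judgement about cause, made by people who know the product, and the two products are a novel device and a familiar medicine. If assessors are readier to attribute a cough or headache to one than to the other, the AR rates differ even when symptom rates are equal. The reverse is also possible: a real excess in one arm can be hidden if its symptoms are more often put down to nicotine withdrawal or a passing illness.

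The analysis cannot repair this. A non-serious symptom that was not judged related is not among the data that 5.3 says will be collected, so a statistical analysis plan has nothing to work with. The protocol itself stresses the need for safety research on EC (1.3), and the AR comparison is one of its seven secondary objectives.

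**Working it through.** The protocol gives no figure to reproduce. The check has two parts: a comparison of the sections, and an illustration on assumed rates.

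**1. The route into the data**

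| Event | Recorded? | Condition | Source |
|---|---|---|---|
| Serious, any cause | Yes | None | 5.4 |
| Non-serious, judged related | Yes, as an AR | Judgement by reporting investigator or Sponsor | 5.1.1, 5.3 |
| Non-serious, not judged related | Not stated | – | 5.3 |

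The quantity compared in 6.4 is AR frequency, so for non-serious events it depends on the second row.

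**2. The list in 5.2.2 against the effects in 1.2**

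Counted separately, the EC safety text in 1.2 names nine effects: throat dryness, throat irritation, mouth dryness, mouth irritation, headache, cough, vertigo, nausea and palpitations. The 5.2.2 list covers two of them (throat irritation and nausea) and leaves out 9 − 2 = 7. Its third item, sleep disturbance, is not among the nine.

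**3. Illustration (hypothetical rates)**

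Input from the protocol: 443 per arm (6.3). Assumed: true symptom incidence t, and attributed shares a (EC) and b (NRT). Recorded rates are p1 = t·a and p2 = t·b. With p̄ = (p1 + p2)/2,

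z = (p1 − p2) / √(2·p̄(1 − p̄)/443).

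With equal true incidence in both arms:

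- t = 30%, shares 60% v 40%: 18% v 12%, p̄ = 0.15, z = 0.06/0.0240 = 2.50, p = 0.012.
- t = 20%, shares 60% v 40%: 12% v 8%, p̄ = 0.10, z = 0.04/0.0202 = 1.98, p = 0.047.
- t = 30%, shares 50% v 45%: 15% v 13.5%, p̄ = 0.1425, z = 0.015/0.0235 = 0.64, p = 0.52.

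The probability of a significant result (two-sided 5%) with no true difference is approximately Φ((|p1 − p2| − 1.96·SE0)/SE1). SE0 is the pooled standard error above and SE1 = √((p1(1 − p1) + p2(1 − p2))/443).

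| True incidence, both arms | Shares 80% v 70% (apparent ratio 1.14) | Shares 80% v 60% (apparent ratio 1.33) |
|---|---|---|
| 10% | 0.08 | 0.21 |
| 20% | 0.13 | 0.40 |
| 30% | 0.19 | 0.59 |
| 50% | 0.34 | 0.88 |

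With equal shares the probability stays at about 0.05.

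Masking works by the same arithmetic. If true incidence were 30% on EC and 20% on NRT, with shares 40% and 60%, the recorded rates would be 0.30 × 0.40 = 12% and 0.20 × 0.60 = 12%.

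**The case against.** The strongest reply is that the protocol is more orderly than a quick reading of 5.2.2 suggests, and much of that reply stands.

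- **A reader might infer that nobody is assigned to judge non-serious events.** The text does not support this. Section 5.1.1 gives the judgement, for all adverse events, to the reporting investigator or the Sponsor. Section 5.2.2 adds named assessors for serious events and does not displace 5.1.1. What remains is that 5.2.2 is silent on non-serious events, so the sections need aligning.
- **A reader might infer that only the three listed reactions are recorded.** The list is not called exhaustive, and 5.3 has every AR documented. The list could equally mean that these three are treated as related in both arms without case-by-case judgement, which would reduce the bias for those items. Its function is unclear, and no more than that can be said.
- **A reader might infer that the comparison measures attribution and not harm.** That goes too far. Serious events are kept whatever their cause, and the AR rate still carries information about harm.
- **Current illness is recorded at baseline and every contact after the quit date (4.8).** Its look-back period is not stated, so it cannot be dismissed as a same-day record. However, nothing links it to the comparison in 6.4.
- **The rates are assumed.** This is correct. The milder scenario gives p = 0.52, and neither the size nor the direction of differential attribution can be taken from the protocol.
- **The CRF is not shown and might contain a common checklist.** That is possible. The rule as written in 5.1.1 and 5.3 would still admit non-serious events to the data only after a causality judgement.

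**Conclusion.** The point holds as a weakness in how the AR outcome is defined. Non-serious events reach the stated data only through a relatedness judgement made with allocation visible, and the resulting rates are compared between arms. The comparison is therefore open to differential attribution that no later analysis can undo.

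Its size is unknown. The illustrations run from negligible (15% v 13.5%, p = 0.52) to a spurious significant difference (18% v 12%, p = 0.012). They show that the mechanism can matter at 443 per arm, not that it will. The conclusion rests on two readings: that 5.3 lists everything to be collected on non-serious events for the AR comparison, and that allocation is open, which is inferred from the product exchange in 4.4 and the absence of any blinding. The primary endpoint is not affected.

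**What to change.** 1. In 4.5, 4.8 and 5.3, record a prespecified symptom list at the contacts already scheduled for adverse reactions (weeks 1 to 4, 24 and 52). It should hold the three items in 5.2.2 plus the effects named in 1.2: mouth or throat dryness or irritation, headache, cough, vertigo and palpitations. Ask in the same words in both arms whether each symptom has occurred since the last contact, grade it on the 5.2.3 severity scale, and record it whatever the presumed cause.
2. In 6.4, base the between-arm comparison on these symptoms. Keep investigator-attributed ARs as a descriptive table.
3. Align 5.1.1, 5.2.2 and 5.3: state who judges non-serious events, and whether the three-item list is a set of examples, a pre-classification or a limit.

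The cost is protocol and CRF wording and one or two more minutes per contact, with no added visits. Recorded counts will be higher in both arms, which the report should explain. Participants still know their allocation when they answer, so some reporting bias will remain and should be stated as a limitation.
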